### **3.3.2 Exclusion Criteria**

#### **1) Target Disease Exceptions**

- a) Subjects with Inclusion Body Myositis, or myositis other than IIM, eg, drug-induced myositis and PM associated with HIV.
- b) Subjects treated with penicillamine or zidovudine in the past 3 months.
- c) Subjects treated with rituximab in the 6 months prior to randomization (there must be laboratory results indicating the presence of circulating B cells (CD19+). Any other biologic treatment in the past 3 months or immune globulin (intravenous [IVIG] or subcutaneous [SCIG]) in the past 3 months prior to randomization.
- d) Subjects with uncontrolled or rapidly progressive interstitial lung disease (at the discretion of the investigator).
- e) Subjects with severe muscle damage (Physician VAS for muscle damage in Myositis Damage Index > 7 cm on a 10 cm scale), permanent weakness due to a non-IIM cause (eg. stroke), or myositis with cardiac involvement.
- f) Cancer-associated myositis (myositis diagnosed within 2 years of a diagnosis of cancer). See criteria (2i)
- g) Subjects who are known to be positive for the anti-TIF1- $\gamma$  (p155/140) autoantibody prior to randomization who were diagnosed with IIM < 1 year prior to randomization.

#### **2) Medical History and Concurrent Diseases**

- a) Subjects with severe pulmonary disease due to IIM requiring supplemental oxygen or who have required mechanical breathing assistance (ventilator) within 1 year of signing informed consent.
- b) Subjects who, at the discretion of the investigator, have severe muscle damage evidenced by severe, clinically apparent muscle atrophy, or persistent weakness without evidence of active inflammatory disease.
- c) Subjects at risk for tuberculosis (TB) defined as follows:
  - i) Current clinical, radiographic or laboratory evidence of active TB, even if currently being treated. Chest X-rays (posterior/anterior and lateral) obtained within the 6 months prior to screening and TB testing (IFN- $\gamma$  release assay or PPD) performed in the past month prior to screening will be accepted; however, a copy of the reports must be placed in the subject binder.
  - ii) A history of active or latent TB unless there is documentation that the subject had received prior anti-TB treatment that was appropriate in duration and type according to local health authority guidelines.
  - iii) Subjects with a positive TB screening test indicative of latent TB will not be eligible for the study unless they:
    - (1) Have no evidence of current TB based on chest X-ray performed during the screening period and by history and physical exam, and
    - (2) They are currently being treated for latent TB or the site has documentation of successful prior treatment of latent TB. Treatment regimens should be dictated by local guidelines as long as the treatment dose and duration meet or exceed local health authority guidelines. If permitted by local guidelines regarding treatment

with biologic medications, subjects with latent TB may be randomized prior to completion of treatment as long as they have completed at least 4 weeks of treatment and they have no evidence of current TB on chest X-ray at screening.

- iv) In some cases, subjects with a positive TB screening test, but no clinical or radiologic evidence of active disease may not require treatment to be eligible for the study (eg, positive TB screening test due to fully treated prior infection). All such cases require approval by the Medical Monitor.
- d) Subjects with recent acute infection defined as:
  - i) Any acute infection within 60 days prior to randomization that required hospitalization or treatment with parenteral antibiotics
  - ii) Any acute infection within 30 days prior to randomization that required oral antimicrobial or antiviral therapy
- e) Subjects with history of chronic or recurrent bacterial infection (such as chronic pyelonephritis, osteomyelitis, bronchiectasis, infection of a joint prosthesis or artificial joint) or serious latent viral infections at the time of enrollment, including subjects with evidence of Immunodeficiency Virus (HIV) infection
- f) Subjects with active systemic fungal infections (eg, histoplasmosis, blastomycosis, or coccidiomycosis)
- g) Subjects with history of recurrent herpes zoster (more than 1 episode/year) or disseminated (more than 1 dermatome) herpes zoster or disseminated herpes simplex, or ophthalmic zoster will be excluded. Symptoms of herpes zoster or herpes simplex must have resolved more than 60 days prior to signing informed consent.
- h) Subjects with history of primary or secondary immunodeficiency
- i) Subjects who have 1) a present malignancy or 2) a previous malignancy within the last 5 years prior to screening (except documented history of cured non-metastatic squamous or basal cell skin carcinoma or cervical carcinoma in situ). Subjects who had a screening procedure that is suspicious for malignancy, and in whom the possibility of malignancy cannot be reasonably excluded following additional clinical, laboratory or other diagnostic evaluations. Additional screening recommendations for malignancy are outlined in [Section 3.3.4](#).
- j) Current symptoms of severe, progressive, or uncontrolled renal, hepatic, hematological, gastrointestinal, pulmonary, psychiatric, cardiac, neurological, or cerebral disease including severe and uncontrolled infections, such as sepsis and opportunistic infections. Concomitant medical conditions that, in the opinion of the investigator, might place the subject at unacceptable risk for participation in this study
- k) Subjects who have received any live vaccines within 3 months of the study drug administration or are scheduled to receive live vaccines during the study. Study subjects also should not be administered a live virus vaccine for a minimum of 3 months following the last dose of study medication. Subjects who are in close contact with others who have received a live vaccine (e.g., live polio vaccine) may be enrolled at the investigator's discretion.
- l) Subjects who have undergone a major surgical procedure, or any surgery that involves the placement of a device or implant, within the 60 days prior to randomization.

- m) Subjects with a history of (within 12 months of signing informed consent), or known current problems with drug or alcohol abuse history or known cirrhosis including alcoholic cirrhosis
- n) Subjects who are impaired, incapacitated, or incapable of completing study related assessments
- o) Subjects who have previously been treated with abatacept.

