##### 3.1.1 Screening Period

Eligibility will be based on specified inclusion and exclusion criteria, medical history, disease activity and safety assessments (see Table 5.1-1). Randomization must occur within four weeks of signing the informed consent. However, subjects may extend the screening period beyond 4 weeks, but not beyond a total of 6 weeks (42 days), from the signing of the informed consent.

Subjects who extend the screening period beyond 4 weeks may be required to repeat some screening assessments. If more than 6 weeks is required, e.g. initiation of treatment for latent TB,

a subject should be screen failed and re-enrolled when appropriate. Screening for malignancy is expected to have been performed prior to the Screening Period ([Section 3.3.4](#)).

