## 5 STUDY ASSESSMENTS AND PROCEDURES

### 5.1 Flow Chart/Time and Events Schedule

**Table 5.1-1: Screening Procedural Outline (IM101611)**

Procedure	Screening Visit	Notes
Eligibility Assessments		
Informed Consent	X	
Call IVRS to Enroll Subject	X	
Inclusion/Exclusion Criteria	X	See Section 3.3
Submit documentation to Adjudication Committee	X	Complete the Active Disease Adjudication Form and submit with supporting documentation, as necessary, see eligibility criteria Section 3.3.1, 2)c)
Medical History	X	
	X	
Safety Assessments		
Physical Examination	X	
Vital Signs	X	Body temperature, seated blood pressure, and heart rate.
Weight and Height	X	
Chest X-ray	X	Required only if the results of a CXR performed within the 6 months prior to screening are not available. A copy of the report must be filed in the subject binder.
Pulmonary Function Testing	X	For subjects with ILD (See Section 5.3.6 )
Serious Adverse Events Assessment		To be reported after signing informed consent
Laboratory Assessments		
TB Screening	X	TB testing (IFN- $\gamma$ release assay or PPD) performed locally within 4 weeks prior to Screening will be accepted. A copy of the report must be filed in the subject binder. See Section 5.3.4 for important details

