### **5.3.4 TB Screening**

A chest X-ray and physical examination are considered part of the process to assess a subject's eligibility. In addition to a chest X-ray that does not show any evidence or suspicion of latent TB, a tuberculin test will be performed and interpreted according to local country Health Authorities and/or Medical Society guidelines. Some guidelines have specific recommendations for subjects who are to receive biologics or immunosuppressant therapies (eg, RA experience with biologic agents), (outside the US sites, local guidelines endorsed by medical societies on PPD testing in subjects with RA being treated with biologics may also apply) or who are immunocompromised and who have had prior BCG vaccination(s). Tuberculin skin testing is not contraindicated for persons who have been vaccinated with BCG. An interferon gamma release assay (eg, QuantiFERON Gold or Tspot/ELISpot) is an acceptable alternative when skin testing for tuberculosis (ie, PPD) is not appropriate. TB screening test may be performed by qualified personnel at the central laboratory or by a qualified local laboratory. If TB test has been performed

within 4 weeks prior to informed consent and clear documentation is available, the test result may be used to screen for eligibility.

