#### **5.3.7.1 X-ray Assessment**

A posterior-anterior and lateral chest X-ray, performed during screening, is required for all subjects unless performed within 6 months prior to obtaining written informed consent and documentation of the earlier X-ray is on file. Investigators must ensure that the results of the chest X-ray satisfy criteria for eligibility. The chest X-ray result will be recorded on the appropriate page of the eCRF. This assessment will not be evaluated by a central lab.

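### For a subject with a positive test indicative of latent TB, Table 5.1-1 and Section 5.3.7.1 of the protocol waive the screening-period chest X-ray that exclusion 2(c)(iii)(1) requires

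*Protocol*

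**What the plan says.** Four pieces of the protocol bear on the film.

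- **Section 3.3.2, exclusion 2(c)(iii).** A subject whose positive screening test indicates latent TB is ineligible unless two conditions are met. Condition (1) is to "Have no evidence of current TB based on chest X-ray performed during the screening period and by history and physical exam". Condition (2) concerns latent-TB treatment. A subject randomized before finishing that treatment may enter as long as "they have completed at least 4 weeks of treatment and they have no evidence of current TB on chest X-ray at screening".
- **Section 3.3.2, exclusion 2(c)(i).** This is the general TB item. It accepts chest films "obtained within the 6 months prior to screening and TB testing" from the past month.
- **Table 5.1-1, chest X-ray row.** The note reads "Required only if the results of a CXR performed within the 6 months prior to screening are not available".
- **Section 5.3.7.1.** A chest film during screening "is required for all subjects unless performed within 6 months prior to obtaining written informed consent", with the earlier film documented on file.

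Section 5.3.4, to which the TB row of Table 5.1-1 refers, opens with "A chest X-ray and physical examination are considered part of the process to assess" eligibility. It says nothing about a new film after a positive test.

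**The concern.** The eligibility criterion fixes when the film must be taken, and the schedule and the procedure text release the site from taking it. Both releases are categorical: the table gives a single circumstance in which a film is needed, and Section 5.3.7.1 covers every subject with one exception. A positive TB test appears in neither. A coordinator working from the table would correctly conclude, on its wording, that no new film is due.

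At stake is the check for active TB before abatacept is added to corticosteroids, an immunosuppressant, or both, in the subjects who most need that check. A subject entered on an older film would also fail an exclusion criterion. Outside the group that has HRCT at baseline, this film is the only chest imaging the protocol ties to the screening period.

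**Working it through.** The plan gives no figure to reproduce. The check compares the texts and then works out how old an accepted film could be.

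**Texts compared, for a subject with a positive test indicative of latent TB and a documented film taken before consent but within 6 months**

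| Provision | Is the earlier film enough? |
|---|---|
| 2(c)(iii)(1) | No. The film must date from the screening period. |
| 2(c)(iii)(2), if randomized before treatment is complete | No. The film must be the one at screening. |
| 2(c)(i) | Accepted as a general rule |
| Table 5.1-1, chest X-ray row | Yes. No new film is called for. |
| Section 5.3.7.1 | Yes. No new film is called for. |
| Section 5.3.4 | Silent on the film's date |

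The criterion gives one answer, and the table and Section 5.3.7.1 give the other.

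**Age of the film at randomization**

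Inputs:
- Screening length, from Section 3.1.1: 4 weeks (28 days) from consent, extendable to 42 days.
- Look-back for an earlier film, from Table 5.1-1 and Section 5.3.7.1: 6 months, taken as 183 days. This is an assumption; calendar half-years run from 181 to 184 days. The table counts back from screening and Section 5.3.7.1 from consent, and I treat these as the same day.

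Formula: age at randomization = days from film to consent + days from consent to randomization.

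| Film taken | 4-week screening | 6-week maximum |
|---|---|---|
| 183 days before consent (edge of window) | 183 + 28 = 211 | 183 + 42 = 225 |
| 91 days before consent (about 3 months) | 91 + 28 = 119 | 91 + 42 = 133 |
| 1 day before consent | 1 + 28 = 29 | 1 + 42 = 43 |
| During screening, as 2(c)(iii)(1) requires | at most 28 | at most 42 |

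With 181 to 184 days for the half-year, the top row becomes 209 to 212 and 223 to 226. At 183 / 6 = 30.5 days per month, 211 days is 6.9 months and 225 days is 7.4 months, so the worst case is about 7 months.

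**Effect on the analysis.** The film enters no endpoint, model or sample-size input. The list of relevant deviations in SAP Appendix 1 contains no TB criterion, so the per-protocol population does not depend on it either.

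**The case against.** The best reply is that the protocol already contains the right answer. Section 3.3 makes the criteria mandatory, and Table 5.1-1 has an inclusion/exclusion row pointing there. Section 5.3.7.1, in the same paragraph as its waiver, tells investigators to make sure that X-ray results meet the eligibility criteria. Section 5.1.1 lets any Table 5.1-1 assessment be repeated, with the latest result before randomization deciding. Section 5.3 requires an eligibility review on Day 1. Section 3.1.1 adds that a subject whose screening runs past 4 weeks may have to repeat some assessments. Subjects identified as having active or relevant ILD, or anti-synthetase syndrome, have an HRCT within 28 days before first dose. The history, examination and treatment conditions of 2(c)(iii) still apply to everyone in the subgroup.

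All of this stands, and it makes an error less likely. None of it orders the new film. The duty in Section 5.3.7.1 concerns the result and not the film's date, and Section 5.1.1 permits a repeat without requiring one.

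A second reply is that the sponsor may have meant the 6-month allowance to cover all of 2(c). That would leave the timing words of (iii)(1) without effect. If it was the intention, (iii)(1) is the text to change. Either way the passages need aligning.

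Three stronger readings may tempt a reader, and the documents do not support them.

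- **That 2(c) contradicts itself.** Item (i) can be read as a general allowance and item (iii) as the stricter rule that controls after a positive test. The conflict lies in the schedule and procedure text.
- **That rescreening has the same gap.** Section 3.1.1 does call for screen failure and re-enrolment "If more than 6 weeks is required, e.g. initiation of treatment for latent TB", and Section 5.1.1 says the chest X-ray may not need repeating. But Section 5.1.1 limits reuse to tests done within the window the protocol defines. For this subgroup that window is the screening period.
- **That every positive test needs a new film.** Item 2(c)(iv) is a separate route, approved case by case by the Medical Monitor, for subjects who "may not require treatment to be eligible for the study". It sets no date for the film.

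**Conclusion.** The inconsistency is real and minor. For a 2(c)(iii) subject with a film from the previous 6 months, Table 5.1-1 and Section 5.3.7.1 waive a film that the exclusion criterion requires. A site following them could randomize on a film about 7 months old at worst (211 to 225 days) where the criterion allows at most 28 to 42 days. A film from the middle of the window would be 119 to 133 days old.

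The upper figures assume a film at the edge of the window, full use of the screening time and a half-year of 183 days. Harm also needs a site that misses 2(c)(iii) at both eligibility checks. How many subjects combine a positive test indicative of latent TB with an earlier film cannot be told from the documents. A reader might infer that subjects with active TB would be enrolled. The documents do not show that; they show only that one safeguard is scheduled incorrectly. The conclusion takes the criterion as the governing text. Power and the primary analysis are unaffected.

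**What to change.** Add this sentence to the chest X-ray note in Table 5.1-1 and to Section 5.3.7.1: *The 6-month allowance does not apply to a subject whose positive TB screening test falls under exclusion 2(c)(iii); such a subject must have a chest X-ray during the screening period.* A pointer in 2(c)(i) is optional. Leave 2(c)(iv) and the rescreening text as they are.

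If the sponsor intended the 6-month window to apply to this subgroup too, it should instead change the timing wording in both conditions of 2(c)(iii). The stricter repair is preferable because it keeps the criterion as written and protects the subjects at issue.

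The cost is one sentence in two places, by protocol clarification or administrative letter. It adds no film beyond the one that 2(c)(iii)(1) already requires.

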### 3) Physical and Laboratory Test Findings

- a) Hepatitis B surface antigen (HBsAg)-positive, *or* Hepatitis B core antibody (HBcAb)-positive subjects with detectable Hepatitis B viral DNA, *and* where required by local regulations or standard practice Hepatitis B surface antibody (HBsAb)-positive subjects with detectable Hepatitis B viral DNA.

#### **NOTE: For Japan only subjects**

Subjects at risk for Hepatitis B virus (HBV), specifically subjects with:

- (1) Hepatitis B surface antigen (+)
- (2) Hepatitis B surface antigen (-) but Hepatitis B surface antibody (+) or Hepatitis B core antibody (+) with Hepatitis B virus DNA  $\geq 1.1$  Log copy /mL(20 IU /mL).

Subjects who are negative HBs antigen but positive anti-HBs antibody or positive anti-HBc antibody with Hepatitis B virus DNA  $< 2.1$  Log copy /mL (20 IU /mL) can be enrolled in the study but must undergo periodic monitoring of HBV DNA and liver enzymes such as AST and ALT. Monitoring should be performed on a monthly basis after initiation of treatment, for six months. After 6 months, interval and duration should be decided at the investigator's discretion and in accordance with local guidelines.

- b) Hepatitis C antibody (HcAb)-positive subjects with detectable Hepatitis C viral RNA
- c) Hemoglobin (Hgb)  $< 8.5$  g/dl
- d) White Blood Count (WBC)  $< 3,000/\text{mm}^3$  ( $3 \times 10^9/\text{L}$ )
- e) Platelets  $< 100,000/\text{mm}^3$  ( $100 \times 10^9/\text{L}$ )
- f) Creatinine clearance  $< 50$  mL/min (Cockcroft-Gault method)
- g) Serum ALT or AST  $> 2$  times upper limit of normal not due to IIM.
- h) Any laboratory test results that, in the opinion of the investigator, might place the subject at unacceptable risk for participation in this study

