**6) MRI Contraindications (for MRI sub-study only)**

For a subject who intends to participate in the MRI sub-study, the radiologist at the site's MRI facility is responsible for determining if a subject is contraindicated from having this procedure. If the subject is contraindicated, the subject must be dropped from the MRI sub-study. The following is a list of some common conditions that may preclude the subject from having MRI of the hands or wrists. However, this should not be used as a substitute for local clinical standards of care. The ultimate decision to perform an MRI on an individual subject in the MRI sub-study rests with the site radiologist, the investigator, and the standard set by the local Ethics Committee:

- a) Subjects who have a history of claustrophobia.
- b) Subjects who have a physical limitation related to fitting in the bore of the magnet (ie, body weight in excess of 250 pounds or 113.4 kilograms).
- c) Subjects with tattoos on the area to be imaged.
- d) Subjects who have a history of allergic reaction to contrast agents
- e) Subjects who had exposure to a radiological contrast agent within the 72 hours prior to the MRI examination.
- f) Subjects who have joint replacements in the leg that is being evaluated by the MRI examination.
- g) Subjects with a pacemaker, epicardial pacemaker wires, MRI-incompatible cardiac valve prostheses, MRI-incompatible vascular clips less than two-months old, or MRI-incompatible aneurysm clips of any age.
- h) Subjects with MRI-incompatible cochlear implants.
- i) Subjects with spinal nerve stimulators.
- j) Subjects with an infusion pump.
- k) Subjects with metallic fragments in the eyes/orbits or in the vicinity of the brain or major neurovascular structures of the body, subjects with an employment history which involves exposure to welding, or subjects who have shrapnel any place in their body.

Eligibility criteria for this study have been carefully considered to ensure the safety of the study subjects and that the results of the study can be used. It is imperative that subjects fully meet all eligibility criteria.

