### **5.3.5 Laboratory Assessments**

All laboratory assessments will be analyzed centrally except where noted.

Blood and/or urine samples will be obtained at all visits noted in Time and Events Schedule. Any laboratory test result that the investigator considers clinically relevant should be recorded on the appropriate Adverse Event page of the CRF (see [Appendix 2](#)).

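### The Japan-only hepatitis B note equates both 1.1 and 2.1 log copy/mL with 20 IU/mL, so at least one figure is wrong and the exclusion and permission overlap on the log-copy scale

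*Protocol*

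**What the plan says.** Protocol Section 3.3.2, Physical and Laboratory Test Findings, carries a note for Japan that adds numerical HBV DNA limits to the global hepatitis B criterion.

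- **Exclusion, item (2).** The group is described as "Hepatitis B surface antigen (-) but Hepatitis B surface antibody (+) or Hepatitis B core antibody (+) with Hepatitis B virus DNA" at or above 1.1 "Log copy /mL(20 IU /mL").
- **Permission, the paragraph that follows.** The group is described as "Subjects who are negative HBs antigen but positive anti-HBs antibody or positive anti-HBc antibody with Hepatitis B virus DNA" below 2.1 "Log copy /mL (20 IU /mL) can be enrolled in the study but must undergo periodic monitoring of HBV DNA and liver enzymes". Monitoring is monthly for six months after treatment starts. After that it is left to the investigator and local guidelines.

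The serology is the same in both sentences. The two sentences differ in the direction of the inequality, as they should, and in the log-copy figure, which they should not. The bracketed IU figure is 20 in both.

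Two other statements bear on how the note is applied. Section 3.3.2 closes with "It is imperative that subjects fully meet all eligibility criteria". Section 5.3.5 says "All laboratory assessments will be analyzed centrally except where noted", and no local-testing exception is noted for the hepatitis tests.

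**The concern.** An exclusion at or above a limit and a permission below a limit should share one limit. Here the permission starts one log higher than the exclusion, while both limits carry the same IU value. Anyone working in log copies would find that a subject between the two figures meets both sentences.

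The limit decides whether someone with serological evidence of past hepatitis B may have abatacept added to corticosteroids, an immunosuppressant or both. If 1.1 is the slip, applying it literally turns away subjects the sponsor meant to accept. If 2.1 is the slip, the permission sentence taken alone would allow viral loads up to ten times the intended limit. Either way, the same enrolment decision could be defended as compliant or cited as a deviation.

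**Working it through.** **Inputs, all from the Japan note in Section 3.3.2**

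- Exclusion: HBV DNA ≥ 1.1 log copy/mL, labelled 20 IU/mL.
- Permission: HBV DNA < 2.1 log copy/mL, labelled 20 IU/mL.
- Serology: the same in both.

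**Step 1: can both labels be right?** Copies/mL = 10^(log copy/mL), and implied copies per IU = copies/mL ÷ 20.

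| Limit | Copies/mL | Implied copies per IU |
|---|---|---|
| 1.1 | 10^1.1 = 12.6 | 12.6 ÷ 20 = 0.63 |
| 2.1 | 10^2.1 = 125.9 | 125.9 ÷ 20 = 6.3 |

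The ratio is exactly 10. No single conversion factor gives 20 IU/mL for both, so at least one pairing is wrong. This step needs no outside figure.

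**Step 2: what do the two sentences do together?**

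| Result in log copy/mL | Item (2) | Next paragraph |
|---|---|---|
| below 1.1 | not excluded | may enrol |
| 1.1 to below 2.1 | excluded | may enrol |
| 2.1 or above | excluded | not covered |

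In IU/mL the rules are complementary: 20 or more is out, below 20 is in. The conflict exists only on the log-copy scale.

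**Step 3: does other text settle it?** The global criterion in Section 3.3.2 turns on whether viral DNA is detectable and gives no number. Section 5.3.5.6, including its Japan note, requires reflex HBV DNA testing and gives no cut-off. Neither document gives a conversion factor, a reporting unit for HBV DNA, or a rule on which unit governs.

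**Step 4: which figure is the likely slip?** This needs a conversion factor, which is an assumption here.

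- At 5 copies per IU, 20 IU/mL is log10(100) = 2.00.
- At 8 copies per IU, 20 IU/mL is log10(160) = 2.20.
- At 1 copy per IU, 20 IU/mL is log10(20) = 1.30.

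The range for 5 to 8 contains 2.1. Even the wider range for 1 to 8 (1.30 to 2.20) never reaches 1.1. The value 1.30 also shows that 1.1 is not simply the logarithm of 20 IU.

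**Step 5: how far off would a literal 1.1 be?** At 8 copies per IU it equals 12.59 ÷ 8 = 1.6 IU/mL, and at 5 it equals 12.59 ÷ 5 = 2.5 IU/mL. The exclusion would then begin at about 1.6 to 2.5 IU/mL instead of 20.

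**Step 6: does the correction work?** With 2.1 in both sentences, or with 1.1 in both, the rules become complementary, with neither overlap nor gap.

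**The case against.** The strongest reply is that a coherent rule is already on the page. Both sentences print 20 IU/mL with complementary inequalities, so anyone working in IU meets no contradiction, and central testing limits differences between sites. That is correct, and it makes the repair easy. It does not make the text right: log copy/mL is the leading unit in both sentences, IU is in brackets, and nothing says which prevails.

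Second, an exclusion can be read as overriding a permission, especially given the closing statement of Section 3.3.2. A subject in the disputed band is then simply excluded, and the literal text errs on the cautious side. This largely stands against the worry about admitting high viral loads. That outcome would require setting item (2) aside and also requires 2.1 to be the slip, which implies 0.63 copies per IU. Other safeguards remain as well: the exclusion for serious latent viral infection, the investigator's discretion to exclude on any laboratory result, and monitoring of antibody-positive subjects who enrol. Over-strict exclusion is the more realistic harm.

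Third, the disputed values differ by one digit in text read from a PDF by a program, so a misread digit cannot be ruled out. Nothing in the text indicates one, and the sponsor can check the source at once.

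Fourth, the reach is narrow: Japan only, one serology group and a one-log band of viral load. That stands.

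**Conclusion.** The concern holds. At least one of the two log-copy figures cannot match its 20 IU/mL label. On the log-copy scale, results from 1.1 to below 2.1 (12.6 to 125.9 copies/mL) meet both the exclusion and the permission. That conclusion rests on the printed figures alone, subject to the digits having been read correctly.

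The view that 1.1 is the wrong figure, and that its literal use would exclude from about 1.6 to 2.5 IU/mL upward, rests on the assumed 5 to 8 copies per IU and should be confirmed clinically. The number of subjects in the band is not stated in the documents.

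The discrepancy affects who may enter in Japan. It does not change which enrolled subjects are monitored, and it does not touch the endpoint, sample size or analysis. It is worth correcting because it sits in an operative safety criterion.

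**What to change.** Use one limit in both sentences of the Japan note: exclude at or above it, and enrol with monitoring below it. The simplest form names 20 IU/mL as the governing value in both places. The log-copy figure should be corrected or deleted once the sponsor's clinical team has confirmed the intended limit. Section 5.3.5.6 needs no change, because its Japan note contains no cut-off.

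The cost is a one-line protocol correction or an administrative letter to the Japanese sites.
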